#### **7.2.9 Physical Examination**

A physical examination will be performed by the investigator or designated physician at the time points specified in the Schedule of Assessments.

Abnormal findings found during screening will be reported on the medical history page of the CRF. Any abnormal findings or worsening findings found after the subject has received etelcalcetide will be reported on the Event CRF.

#### **7.2.10 Electrocardiograms**

Subject must be in supine position in a rested and calm state for at least 5 minutes before ECG assessment is conducted. If the subject is unable to be in the supine position, the subject should be in most recumbent position as possible. All measurements will be obtained prior to hemodialysis.

A single 12-lead ECG will be performed at timepoints designated in the Schedule of Assessments ([Table 1](#)). Data will be reported on the CRF. The ECG must include the following measurements: Heart Rate, QRS, QTc, and PR intervals.

The PI will review all ECGs. Once signed, the original ECG tracing will be retained with the subject's source documents. At the request of the sponsor, a copy of the original ECG will be made available to Amgen.

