**Treatment-Related AE:**

A treatment-related AE is any treatment-emergent AE that per investigator's review has a reasonable possibility of being caused by the investigational product.

Baseline

For any variable, unless otherwise defined, baseline is the last assessment taken prior to the first investigational product administration.

Baseline iPTH, cCa, total calcium, ionized calcium are defined as the average of screening and Day -2 assessments. If not all the values are available, the average will be calculated based on available value(s).

Baseline pre-dialysis ECG parameters including PR, QRS, QT, QTcB and QTcF are defined as the average of last non-missing pre-dialysis screening assessment and Study Day -2 pre-dialysis assessment.

---

The use of concomitant medication of interest at baseline is defined as use of each concomitant medication on Study Day 1. This includes medication use that starts prior to Study Day 1 and ends on Study Day 1 or duration of use covers Study Day 1.

Change from Baseline

The arithmetic difference between a post-baseline value and the baseline value:

Change (absolute) from Baseline = (Post-baseline Value – Baseline Value)

Percent change from Baseline

Percent Change from Baseline = [(Post-baseline Value – Baseline Value) / Baseline Value] x 100

Body Mass Index (BMI)

BMI will be calculated as weight (kg)/ [height (m)] in the clinical database.

Corrected (Bazett) QT Interval (QTcB)

The Bazett correction will be calculated from the investigator reported QT (msec) and RR interval (msec) (QTcB=QT/(RR/1000)0.50).

Corrected (Fridericia) QT Interval (QTcF)

The Fridericia correction will be calculated from the investigator reported QT (msec) and RR interval (msec) (QTcF=QT/(RR/1000)0.33).

End-of-Study

The EOS is the last planned clinical visit for each subject enrolled in this study. The last planned visit day for subjects in cohort 1 and 2 is on Study Day 30.

Subject-level End of Study (EOS) Date

End of study for each subject is defined as the date the subject last participated in the study. The date will be recorded on the End of Study CRF page.

Enrollment

A subject will be considered enrolled when the Investigator decides that the subject has met all eligibility criteria. Enrollment Date is defined as the date collected on the CRF.

Investigational Product

The term investigational product is used in reference to etelcalcetide.

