#### **10.5.4        Electrocardiogram (ECG)**

Summaries over time and/or changes from baseline over time will be provided for all ECG parameters including PR, QRS, QT, QTcF and QTcB.

Subjects will be categorized into the following groups per their maximum change from baseline in QTcF and QTcB. Unscheduled assessments will be included in the determination of the maximum change.

- <=30 msec
- >30 – 60 msec
- >60 msec

The number and percentage of subjects in each group will be summarized.

Subjects will also be categorized into the following groups per their maximum post-baseline QTcF and QTcB. Unscheduled assessments will be included in the determination of the maximum post baseline value.

- <=450 msec
- >450 – 480 msec
- >480 – 500 msec
- >500 msec

The number of subjects in each group will be summarized for each cohort. All on-study ECG data will be listed.

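### Does leaving uncorrected QT off the protocol's list of ECG measurements stop the SAP from deriving QTcB and QTcF?

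*Protocol*

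**What the plan says.** Protocol 7.2.10 calls for a single 12-lead ECG at each scheduled time and sets the minimum content: "The ECG must include the following measurements: Heart Rate, QRS, QTc, and PR intervals". It names no correction formula for that QTc. The same section has results entered on the CRF and the signed tracing kept with the source documents, with a copy available to the sponsor on request. Bazett is prescribed only in exclusion criterion 212, for the screening eligibility limit.

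SAP Section 6 (Definitions) derives both corrections from raw intervals. For QTcB: "The Bazett correction will be calculated from the investigator reported QT (msec) and RR interval (msec"), with exponent 0.50. For QTcF: "The Fridericia correction will be calculated from the investigator reported QT (msec) and RR interval (msec"), with exponent 0.33. It also sets a baseline: "Baseline pre-dialysis ECG parameters including PR, QRS, QT, QTcB and QTcF are defined as the average" of the last non-missing screening value and the Day -2 value.

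SAP 10.5.4, under Primary Endpoints, states: "Summaries over time and/or changes from baseline over time will be provided for all ECG parameters including PR, QRS, QT, QTcF and QTcB". It then groups subjects by maximum change and by maximum level: "Subjects will also be categorized into the following groups per their maximum post-baseline QTcF and QTcB". For the level it adds: "Unscheduled assessments will be included in the determination of the maximum post baseline value".

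Table 1 of the protocol schedules three ECGs: screening, Day -2 and Day 30.

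**The concern.** The SAP names an input, QT, that the protocol's list of compulsory measurements omits. ECG change belongs to the second primary endpoint, and protocol 2.3 names QTc prolongation among the events that can follow hypocalcaemia, the drug's most important risk. Day 30 is the only scheduled ECG after dosing. If a site entered only the listed items and QT were never retrieved, that subject would drop out of the post-baseline QT, QTcB and QTcF summaries unless an unscheduled ECG existed. One such subject leaves 4 of 5 in a minimum-size cohort, or 9 of 10 overall.

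The listed items do not obviously close the gap. QT can be worked back from QTc and heart rate only if the correction formula is known, and with about 15 sites a common formula cannot be taken for granted. SAP Section 11 declares no departures from the protocol, so it does not flag the difference.

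**Working it through.** Neither document states a figure to reproduce. The check compares the texts and then asks whether the missing item can be recovered.

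**Step 1. What the SAP needs and what the protocol lists.**

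| Item used in the SAP | On the 7.2.10 list? | Other route |
|---|---|---|
| PR, QRS | Yes | not needed |
| RR | No | RR = 60000/HR (ms); heart rate is listed |
| QT | No | CRF field, the site's own QTc calculation, or the retained tracing |
| QTcB, QTcF | Only an unspecified QTc | computed from QT and RR |

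Only QT is in question, and through it the two corrected values.

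**Step 2. Can QT be worked back from QTc and heart rate?** Inverting the SAP formulas gives QT = QTc × (RR/1000)^0.50 if the reported QTc is Bazett, and QT = QTc × (RR/1000)^0.33 if it is Fridericia. Assume a reported QTc of 450 ms and the heart rates below. These values are illustrative and do not come from the documents. At 100/min, RR = 60000/100 = 600 ms, so QT = 450 × 0.6^0.50 = 348.6 ms or 450 × 0.6^0.33 = 380.2 ms.

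| Heart rate (/min) | RR (ms) | QT if Bazett (ms) | QT if Fridericia (ms) | Gap (ms) |
|---|---|---|---|---|
| 60 | 1000 | 450.0 | 450.0 | 0.0 |
| 70 | 857 | 416.6 | 427.7 | 11.1 |
| 80 | 750 | 389.7 | 409.2 | 19.5 |
| 100 | 600 | 348.6 | 380.2 | 31.6 |
| 120 | 500 | 318.2 | 358.0 | 39.8 |

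Without the formula, back-calculation is unsafe at faster heart rates. With it, QT is exact. At 100/min with Bazett, QT = 348.6 ms, and the SAP then gives QTcB = 348.6/0.6^0.50 = 450.0 ms and QTcF = 348.6/0.6^0.33 = 412.6 ms.

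**Step 3. Does the plan rely on back-calculation, or on the reported QTc standing in for QTcB or QTcF?** No. SAP Section 6 computes both from QT and RR. The gaps above show why nobody should guess the formula. They are not errors that the planned analysis would make.

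**Step 4. Is QT likely to be absent?** The 7.2.10 list says what an ECG has to contain and does not exclude more. A QTc is a QT divided by a power of RR, so a site that reports QTc and heart rate has already determined QT. The SAP describes QT and RR as investigator-reported, which points to CRF fields for them.

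**Step 5. Size.** If the CRF collects QT, 0 ECGs are affected. If it does not, up to 3 scheduled ECGs × 10 subjects = 30 tracings would have to be read again. Screening cannot be left out of that count, because criterion 212 fixes Bazett for the eligibility test and not for the QTc entered under 7.2.10. Each of these tracings is to be retained.

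**The case for a change.** The best case for acting is that the protocol is what sites follow, that its list omits the one interval from which both corrected values are built, and that adding it would cost a word or two and no extra ECG. With a single scheduled post-dose ECG and cohorts that may hold only 5 subjects, each missing value counts. There is also a related gap in the SAP. For iPTH and calcium it says "If not all the values are available, the average will be calculated based on available value(s"), but it gives no such rule for the ECG baseline if the Day -2 value is missing.

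The mismatch in wording stands, and so does the point that QT cannot be recovered from a QTc of unknown formula. What does not stand is the step from there to lost data. That step requires the CRF to lack a QT field, the site to record nothing beyond the list, and nobody to consult the retained tracing. The documents support none of these, and the SAP's wording speaks against the first. The missing rule for the ECG baseline is a separate matter that does not depend on 7.2.10, and an analyst with one of the two values would ordinarily use it.

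**Conclusion.** The concern is accurate as a reading of the two texts, but it does not call for a change. It is a gap in detail that is filled sensibly in practice: the list in 7.2.10 is a minimum, the SAP treats QT and RR as reported data, RR follows from heart rate, and the tracing allows any missed QT to be read later. Confirming that the ECG form carries QT is ordinary data-management work and needs no plan text.

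The effect on results is none if the CRF collects QT. If it does not, the cost is re-reading up to 30 tracings for 10 subjects, with no loss as long as they are retained as required. No hypothesis is tested, PR and QRS are untouched, and no stated figure moves.

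This rests on two assumptions: that the SAP's description of QT and RR as investigator-reported reflects the CRF, which is not among the documents, and that tracings are kept as 7.2.10 requires. If the first fails, the second is enough.

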#### **7.2.11 Clinical Laboratory Safety Assessments**

Blood sampling (not to exceed 5.6 mL) for safety laboratory testing will be conducted at time points designated in the Schedule of Assessments. Results will be reported on the CRF. [Table 2](#) below outlines the panel of analytes required for safety laboratory testing.

**Table 2. List of Analytes**

Chemistry	Hematology
Sodium	Hemoglobin
Potassium	Hematocrit
Chloride	Mean corpuscular volume
Bicarbonate (HCO 3 )	Platelets
Total protein	White blood cell differentials
Albumin	

• Total neutrophils

Calcium a	

• Eosinophils

PTH	

• Basophils

Magnesium	

• Lymphocytes

Phosphorus	
Blood urea nitrogen (BUN)	
Creatinine	
Uric Acid	
Total bilirubin	
Direct bilirubin	
Alkaline phosphatase	
Alanine aminotransferase (ALT) (SGPT)	
Aspartate aminotransferase (AST) (SGOT)	

aTo include total calcium, albumin-corrected calcium, and ionized calcium

### **7.2.12 Pharmacodynamic Measurements**

Measurements of serum calcium (total calcium, albumin corrected calcium and ionized calcium) and PTH determinations will be collected at time points designated in the Schedule of Assessments ([Table 1](#)).

The calcium level determinations described in this section are derived from the samples drawn as part of the Clinical Laboratory Safety Assessments described in [Section 7.2.11](#). Results will be reported in the CRF. Approximate blood draw volumes are shown in [Table 3](#).

### **7.2.13 Pharmacokinetic Measurements**

Blood samples (0.15 mL) for the determination of etelcalcetide PK parameters will be collected at time points designated in the Schedule of Assessments. Study site staff will complete a shipping log that will include subject identification information and the time and date of collection of each sample. Detailed instructions on sample collection, storage and shipment to the central laboratory are provided in a separate Sample Collection Notebook.

#### 7.2.14 Anticipated Blood Collection Volumes

It is anticipated that subjects enrolled in this study with weights greater than 12 kg will be asked to donate approximately 28.8 mL of blood over the course of the study period (see [Table 3](#) for estimated volumes). At screening approximately 5.6 mL of blood will be drawn for safety laboratory assessments (including Baseline PD endpoints). Females of child bearing potential will have an additional blood sample (0.5 mL) obtained for serum pregnancy testing at screening. On Day -2 (Baseline) approximately 3.6 mL of blood will be drawn for antibody (0.45 mL) and safety lab/PD endpoints (3.1 mL). On Day 1 and at each safety follow up visit (Day 3, 5 (or 6), 8 and 10), approximately 0.15 to 3.3 mL will be drawn. Approximately 6.2 mL of blood will be drawn for antibody (0.45 mL), PK (0.15 mL) and safety laboratory assessments (5.6 mL) at the end of study visit.

Subjects that weigh 7 to 12 kg will be asked to donate smaller amounts of blood, approximately 16.7 mL. At screening approximately 2.8 mL of blood will be drawn for safety laboratory assessments (including Baseline PD endpoints). Female subjects weighing 12 kg or less are not anticipated to be of child bearing potential and therefore will not require a serum pregnancy test. On Day -2 (Baseline) approximately 2.3 mL of blood will be drawn for antibody (0.45 mL) and safety lab/PD endpoints (1.8 mL). On Day 1 and at each safety follow up visit (Day 3, 5 (or 6), 8 and 10), approximately 0.15 to 2.1 mL will be drawn. Approximately 3.4 mL of blood will be drawn for antibody (0.45 mL) safety laboratory assessments (2.8 mL) at the end of study visit.

Specified blood volumes are approximate and may vary, however, per individual, the study-related blood loss (including any losses in the maneuver) will not exceed 3% of the total blood volume during a period of four weeks and will not exceed 1% at any single time per regulatory guidance on paediatric clinical trials.

**Table 3. Approximate Blood Draw Volume**

Sample	Volume (mL) Subject Weight > 12 kg	Volume (mL) Subject Weight 7-12 kg	No of Samples All Subjects	Total Volume (mL) Subject Weight > 12 kg	Total Volume (mL) Subject Weight 7 – 12 kg
Safety Lab Tests (including Calcium, PTH)	5.6	2.8	2	11.2	5.6
cCA, albumin, PTH	3.1	1.8	5	15.5	9
PK	0.15	0.15	8	1.2	1.2
Antibody	0.45	0.45	2	0.9	0.9
Total				28.8	16.7

### **7.3 Antibody Testing Procedures**

Blood sample(s) for Antibody testing are to be collected at Baseline (Day -2) and at EOS (Schedule of Assessments, [Table 1](#)) for the measurement of anti-etelcalcetide binding antibodies. Samples testing positive for binding antibodies may also be tested for neutralizing antibodies and may be further characterized for quantity/titer, isotype, affinity and presence of immune complexes. Additional blood samples may be obtained to rule out anti-etelcalcetide antibodies during the study.

Subjects who test positive for binding, non-neutralizing antibodies and have clinical sequelae that are considered potentially related to an anti-etelcalcetide antibody response may also be asked to return for additional follow-up testing.

Refer to the Schedule of Assessments ([Table 1](#)), as applicable, for specific time points and the laboratory manual for detailed collection and handling instructions.

### **7.4 Sample Storage and Destruction**

Any blood PK or antibody sample collected according to the Schedule of Assessments ([Table 1](#)) can be analyzed for any of the tests outlined in the protocol and for any tests necessary to minimize risks to study subjects. This includes testing to ensure analytical methods produce reliable and valid data throughout the course of the study. This can also include, but is not limited to, investigation of unexpected results, incurred sample reanalysis, and analyses for method transfer and comparability.

All samples and associated results will be coded prior to being shipped from the site for analysis or storage. Samples will be tracked using a unique identifier that is assigned to the samples for the study. Results are stored in a secure database to ensure confidentiality.

If informed consent is provided by the subject's LAR, Amgen can do additional testing on remaining samples (ie, residual and back-up) to investigate and better understand the secondary hyperparathyroidism due to chronic kidney disease, the dose response and/or prediction of response to etelcalcetide, characterize antibody response, and characterize aspects of the molecule (eg, mechanism of action/target, metabolites). Results from this analysis are to be documented and maintained, but are not necessarily reported as part of this study. Samples can be retained for up to 20 years.

Since the evaluations are not expected to benefit the subject directly or to alter the treatment course, the results of other exploratory studies are not placed in the subject's medical record and are not to be made available to the subject, members of the family, the personal physician, or other third parties, except as specified in the informed consent.

The subject retains the right to request that the sample material be destroyed by contacting the investigator. Following the request from the subject, the Investigator is to provide the sponsor with the required study and subject number so that any remaining blood samples and any other components from the cells can be located and destroyed. Samples will be destroyed once all protocol-defined procedures are completed. However, information collected from samples prior to the request for destruction, will be retained by Amgen.

The sponsor is the exclusive owner of any data, discoveries, or derivative materials from the sample materials and is responsible for the destruction of the sample(s) at the request of the subject through the investigator, at the end of the storage period, or as appropriate (eg, the scientific rationale for experimentation with a certain sample type no longer justifies keeping the sample). If a commercial product is developed from this research project, the sponsor owns the commercial product. The subject has no commercial rights to such product and has no commercial rights to the data, information, discoveries, or derivative materials gained or produced from the sample.

See [Section 11.3](#) for subject confidentiality.

## 8. WITHDRAWAL FROM TREATMENT, PROCEDURES, AND STUDY

### 8.1 Subjects' Decision to Withdraw

Subjects have the right to withdraw from the study at any time and for any reason without prejudice to their future medical care by the physician or at the institution.

Subjects (or a legally acceptable representative (LAR)) can decline to continue receiving investigational product and/or other protocol required therapies or procedures at any time during the study but continue participation in the study. If this occurs, the investigator is to discuss with the subject the appropriate processes for discontinuation from investigational product or other protocol required therapies and must discuss with the subject the options for continuation of the Schedule of Assessments ([Table 1](#)) and collection of data, including endpoints and adverse events. The Investigator must document the change to the Schedule of Assessments ([Table 1](#)) and the level of follow-up that is agreed to by the subject (eg, in person, by telephone/mail, through family/friends, in correspondence/communication with other physicians, from review of the medical records).

Withdrawal of consent for a study means that the subject (or a LAR) does not wish to receive further protocol-required therapies or procedures, and the subject (or a LAR) does not wish to or is unable to continue further study participation. Subject data up to withdrawal of consent will be included in the analysis of the study, and where permitted, publically available data can be included after withdrawal of consent. The investigator is to discuss with the subject appropriate procedures for withdrawal from the study.

### 8.2 Investigator or Sponsor Decision to Withdraw or Terminate Subjects' Participation Prior to Study Completion

The investigator and/or sponsor can decide to withdraw a subject(s) from investigational product and/or other protocol required therapies, protocol procedures, or the study as a whole at any time prior to study completion.

Subjects may be eligible for continued treatment with Amgen investigational product(s) and/or other protocol required therapies by a separate protocol or as provided for by the local country's regulatory mechanism, based on parameters consistent with [Section 12.1](#).

### **8.2.1 Reasons for Removal From Treatment**

Reasons for removal from protocol-required investigational product(s) or procedural assessments include any of the following:

- subject request
- safety concern (eg, due to an adverse event, ineligibility determined, protocol deviation, non-compliance, requirement for alternative therapy, protocol-specified criteria (list criteria), pregnancy)
- death
- lost to follow-up
- decision by sponsor (other than subject request, safety concern, lost to follow-up)

### **8.2.2 Reasons for Removal From Study**

Reasons for removal of a subject from the study are:

- decision by sponsor
- withdrawal of consent from study
- death
- lost to follow-up

## **9. SAFETY DATA COLLECTION, RECORDING, AND REPORTING**

### **9.1 Definition of Safety Events**

#### **9.1.1 Adverse Events**

An adverse event is defined as any untoward medical occurrence in a clinical trial subject. The event does not necessarily have a causal relationship with study treatment. The investigator is responsible for ensuring that any adverse events observed by the investigator or reported by the subject are recorded in the subject's medical record.

The definition of adverse events includes worsening of a pre-existing medical condition. Worsening indicates that the pre-existing medical condition or underlying disease has increased in severity, frequency, and/or duration more than expected by the investigator's assessment. A pre-existing condition that has not worsened more than anticipated (ie, more than usual fluctuation of disease) during the study, or involves an intervention such as elective cosmetic surgery or a medical procedure while on study, is not considered an adverse event.

The investigator's clinical judgment is used to determine whether a subject is to be removed from treatment due to an adverse event. In the event a subject, or subject's legally acceptable representative requests to withdraw from protocol-required therapies or the study due to an adverse event, refer to [Section 8.1](#) for additional instructions on

the procedures recommended for safe withdrawal from protocol-required therapies or the study.

